4.6.3. Adverse Events and Serious Adverse Events

Adverse events (AE) and Serious Adverse Events (SAE) will be collected from the time of informed consent signature and then at each visit until the end of follow-up period. All AEs are to be coded to a PT and associated primary SOC according to the MedDRA[®] (the latest current available version).

An AE is any untoward medical occurrence in a patient administered a study drug which may or may not have a causal relationship with the study drug. Therefore, an AE is any unfavorable and

unintended sign (including abnormal laboratory finding), symptom, or disease which is temporally associated with the use of a study drug, whether or not considered related to the study drug. An AE also includes any worsening (ie, any clinically significant change in frequency and/or intensity) of a pre-existing condition that is temporally associated with the use of the study drug.

A SAE is an AE that is classified as serious according to the criteria specified in the protocol.

The criteria for determining whether an abnormal objective test finding should be reported as an AE include:

- the test result is associated with accompanying symptoms, and/or
- the test result requires diagnostic testing and medical/surgical intervention, and/or
- the test result leads to a change in dosing (outside of protocol-stipulated dose adjustments), discontinuation from study, significant additional concomitant drug treatment, or other therapy.

4.6.4. Adverse Events of Special Interest

Adverse events of special interest (AESI) are AEs (serious or non-serious) required to be monitored, documented, and managed in a pre-specified manner as described in the protocol. In this study, the AESI are listed below (as provided in the protocol):

- Adjudicated Arthropathy (as confirmed by adjudication) selected using an eCRF specific tick box on the AE page.
- Sympathetic nervous system dysfunction (as diagnosed after consultation with an appropriate specialist, such as a neurologist and/or a cardiologist) selected using an eCRF specific tick box on the AE page.
- Peripheral sensory AEs that require a neurology or other specialty consultation selected using an eCRF specific tick box on the AE page.
- Joint replacement surgery (defined as elective joint replacement surgery not due to new or worsening AE) using eCRF specific tick box on the AE page.

4.6.5. Laboratory Safety Variables

The clinical laboratory data consists of serum chemistry, hematology, urinalysis and urine electrolytes. Samples for laboratory testing will be collected at the time points specified in the Schedule of Events ([Appendix 10.1](#)).

Clinical laboratory values will be in standard international (SI) units, including associated normal ranges provided by the central laboratory, and grouped by function in summary tables.

Clinical laboratory values in conventional (US) units will also be available in the database, with associated normal ranges.

Both actual test values and “change from baseline” values (defined as the post-baseline value minus the baseline value) will be used in central lab result summaries. Potentially clinically significant values (PCSV) ranges will be applied to central lab test values as applicable (see [Appendix 10.2](#) for PCSV definitions).

4.6.6. Vital Signs

The following vital signs parameters will be collected according to the Schedule of Events in [Appendix 10.1](#):

- Body temperature (°C)
- Supine/standing systolic and diastolic blood pressures (mmHg) and pulse (bpm)
- Respiratory rate (breaths per minute)

Both actual values and “change from baseline” values (defined as the post-baseline value minus the baseline value) will be used in the result summaries. PCSV ranges will be applied to the vital sign parameter values as applicable (see [Appendix 10.2](#) for PCSV definitions).

4.6.7. Orthostatic Hypotension

A patient will be determined to have orthostatic hypotension if any of the following criteria are met:

- If the supine blood pressure is <160 mmHg systolic, a decrease in either the 1 or 3 minute standing systolic blood pressure of ≥ 20 mmHg or a decrease in the standing diastolic blood pressure of ≥ 10 mmHg from the supine systolic or diastolic blood pressure

OR

- If the supine blood pressure is ≥ 160 mmHg systolic, a decrease in either the 1 or 3 minute standing systolic blood pressure of ≥ 30 mmHg or a decrease in the standing diastolic blood pressure of ≥ 15 mmHg from the supine systolic or diastolic blood pressure

OR

- An increase in either the 1 or 3 minute standing heart rate of ≥ 30 bpm from the supine heart rate

OR

- The patient is unable to stand for either one of the standing blood pressure measurements due to dizziness or lightheadedness

Confirmed orthostatic hypotension is defined as initial assessment meeting the above orthostatic hypotension criteria confirmed by subsequent repeated assessments per protocol.

4.6.8. 12-Lead Electrocardiography

A standard 12-lead ECG will be performed according to the Schedule of Events in [Appendix 10.1](#). Heart rate will be recorded from the ventricular rate, and the PR, QRS, and QT, QTc intervals, and ECG status (normal, abnormal not clinically significant or abnormal clinical significant) will also be recorded.

QTcF and QTcB are defined as follows:

$$QTcF (ms) = QT/RR^{1/3} \text{ and } QTcB (ms) = QT/RR^{1/2},$$

where QT is the uncorrected QT interval measured in ms, and RR is 60/HR with HR being the heart rate in beats per minute.

PCSV ranges will be applied to the ECG parameter values as applicable (see [Appendix 10.2](#) for PCSV definitions).

4.6.9. Physical and Neurological Examination Variables

Patients will have a thorough and complete physical examination including an examination of the knees, hips, and shoulders performed according to the Schedule of Events in [Appendix 10.1](#). The result for each body system is an outcome of normal or abnormal (clinically significant, or not clinically significant). Neurological evaluations will cover the following domains: motor, sensory, cranial nerves, reflexes and coordination/balance and assessment for presence/absence of signs of carpal tunnel syndrome. The results of each specific domains will be described as normal or abnormal (clinically significant, or not clinically significant) with the exception of the carpal tunnel evaluation which will be described as present/absent.

4.6.10. Biomarker variables

Biomarker analysis will be described in a separate biomarker SAP.

4.6.11. Other Safety Variables

Other safety endpoints include:

- Survey of Autonomic Symptoms questionnaire:
 - The Survey of Autonomic Dysfunction serves as a monitoring tool throughout the study to prompt further evaluation of potential events of sympathetic nervous system dysfunction, as deemed necessary at the investigator's discretion. The survey asks if patients have a symptom, to what extent they are bothered by it.

The extent to which symptoms are bothersome are described in 5 categories (not at all, a little, some, moderate, a lot).

- Summaries will include the number and proportion of patients presenting with symptoms at scheduled timepoints by degree of bothersomeness. Change from baseline in the degree of bothersomeness of each symptom represented will also be presented at scheduled timepoints. Change from baseline in the degree of bothersomeness will be described as better, same or worse.
- Joint Pain Questionnaire:
 - Number of subjects with significantly worse joint pain in any joint at each scheduled visit
 - Number of subjects with significantly worse joint pain by joint at each scheduled visit
- Joint space width for the affected joints as well as other knee or hip joints at each scheduled visit (taken from bilateral x-rays).
- All-cause JR:
 - Number and percentage of patients with JR (all-cause JRs)
 - Reason for JR (all-cause JRs)
 - Time to JR (all-cause JRs)
- Adjudicated Arthropathy (AA):
 - Number and percentage of patients with AA
 - Number and percentage of patients meeting Destructive Arthropathy criteria (DA)
 - Subtypes of AA
 - Time to AA
 - Time to DA

4.7. Pharmacokinetic Variables

The PK variable will be fasinumab concentrations in serum at specified sampling time points.

4.8. Anti-Drug Antibody Variables

The immunogenicity variables are ADA status, titer, at each time-point/visit. Serum samples for ADA will be collected at the clinic visits specified in [Appendix 10.1](#).

5. STATISTICAL METHODS

For continuous variables, descriptive statistics will include the following information: the number of patients reflected in the calculation (n), mean, median, SD, minimum, 1st & 3rd quartiles (Q1 & Q3), and maximum.

For categorical or ordinal data, frequencies and percentages will be displayed for each category.

Period of Observation - Unless otherwise stated, analysis of all safety and non-safety variables captured at multiple visits will be analyzed by the following observation periods:

- The *Pre-Treatment Period* is defined as the time from signing the ICF to before the first dose of study drug.
- The *On-Treatment Period* is defined as the time from the first dose of study drug up to 28 days after the last dose of study drug.
- The *Follow-Up/Post-Treatment Period* is defined from the end of the On-Treatment Period to the date of the follow-up clinic visit (Week 36 visit) or early termination date.

5.1. Demographics and Baseline Characteristics

Demographic and baseline characteristics described in Section 4.1 will be descriptively summarized by treatment group and overall for the study based on FAS.

5.2. Medical History

All reported patient's medical history and surgical history will be descriptively summarized by primary SOC and PT by treatment group and overall for the FAS. The tables will be sorted by decreasing frequency of primary SOC in the fasinumab group. Within each primary SOC, PTs will be sorted by decreasing frequency in the fasinumab group.

5.3. Prior/Concomitant Medications

Prior Medications

All prior medications, dictionary coded by WHO, will be descriptively summarized by treatment group based on the FAS. Summaries will present number and percentage of patients for all prior medications, by decreasing frequency of the fasinumab group incidence of ATC followed by ATC level 2, ATC level 4 and PT. In case of equal frequency across anatomic or therapeutic categories, alphabetical order will be used. Patients will be counted once in each ATC category (anatomic or therapeutic) linked to the medication but may be counted several times for the same medication.

Concomitant Medications

All concomitant medications, dictionary coded by WHO, will be descriptively summarized by treatment group based on the SAF. Summaries will present number and percentage of patients for the concomitant medication groups described in Section 4.3 for all concomitant medications, by decreasing frequency of the fasinumab group incidence of ATC followed by ATC level 2, ATC level 4 and PT. In case of equal frequency across anatomic or therapeutic categories, alphabetical order will be used. Patients will be counted once in each ATC category (anatomic or therapeutic) linked to the medication, hence may be counted several times for the same medication.

The following will be summarized:

- Prior Medications
- Concomitant medications
- Post-treatment medications
- On-study (Concomitant + Post-Treatment) Medications

When medication start/end date is missing, the rules for determining whether a medication is prior, concomitant, or post-treatment, are specified in Section 6.3.

5.4. Prohibited Medications

Number and percentage of patients with prohibited medications will be descriptively summarized by treatment group based on the SAF. The tables will be sorted by decreasing frequency of ATC Level 2, ATC Level 4, and PT in the fasinumab group.

The number of patients with NSAIDs use during treatment period will be summarized by treatment group based on the SAF.

Total NSAIDs-use days during each treatment period and follow-up period (before AA for patients with AA) will be summarized by treatment group for patients in the SAF. Additionally, days from last study drug dose to first NSAID dose will be summarized by treatment group for patients in the SAF.

5.5. Subject Disposition

The disposition of patients in the study will be summarized by treatment group and overall for FAS. The following will be provided:

- The total number of screened patients: signed the Informed consent form (ICF)
- The total number of randomized patients: received a randomization number
- The total number of patients in each analysis set

- The total number of patients who discontinued the study, and the reasons for discontinuation
- The number of patients who completed study treatment, patients who discontinued treatment and reason for treatment discontinuation
- A listing of patients treated but not randomized, patients randomized but not treated, and patients randomized but not treated as randomized
- A listing of patients prematurely discontinued from treatment, along with reasons for discontinuation
- A listing of patients who withdrew from the study, along with reasons for study withdrawal

5.5.1. Screening Disposition

In the summaries below, percentages will be calculated using the number of screened patients as the denominator. Summaries will present the overall frequencies (and percentages as applicable) for the following:

- Screened patients (defined as having signed the ICF).
- Patients randomized (defined in the protocol as having received a randomization number).
- Patients that did not meet the inclusion/exclusion criterion but were randomized (if applicable).
- Patients treated but not randomized (if applicable).
- Screen Fail patients: broken out by reason for screen failure.

Additionally, the following listings will be provided (if applicable):

- Listing of Patients Treated but not Randomized.
- Listing of Screening Failures and reasons for all screen failing

5.5.2. Treatment and Study Disposition

Unless otherwise noted, percentages will be calculated using the number of patients in the FAS as the denominator. Summaries will present the frequencies (and percentages as applicable) by treatment group for the following:

- Patients randomized (defined as having received a randomization number). This row will reflect the grouping based on randomization assignment.

- Patients randomized and treated.
- Patients randomized but not treated. This row will reflect grouping based on randomization assignment.
- Patients who completed study treatment period.
- Patients who discontinued treatment, and reason for treatment discontinuation.
- Patients who completed the study.
- Patients who withdrew from the study, and reason for study withdrawal.

A Kaplan-Meier plot of time to treatment/study discontinuation by treatment group will be provided.

5.6. Extent of Study Treatment Exposure and Compliance

The analysis population is based on the SAF.

5.6.1. Treatment Compliance

Overall treatment compliance to the SC study drug injection is defined as the actual number of SC injections divided by the expected number of SC injections during the on-treatment period up to treatment discontinuation. It is calculated according to the following formula:

$$\frac{\text{Number of actual injections of study drug received during the treatment exposure period}}{\text{Number of planned injections of study drug during the treatment exposure period on or before the time that the patient discontinued from the treatment phase of the study}} \times 100$$

The total number of SC injections will be summarized by treatment groups via descriptive statistics based on the SAF. A summary of the number (and percentage) of patients categorized by the number of SC injections received will also be included.

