7. STUDY TREATMENTS

7.1. Investigational and Reference Treatments

Fasinumab drug product is supplied for this study in the following concentrations:

- Fasinumab 2 mg/mL: Each 1 mL single-use pre-filled syringe delivers 0.5 mL of 2 mg/mL solution to provide a 1 mg dose of study drug
- Fasinumab-matching placebo: Each 1 mL single use pre-filled syringe delivers 0.5 mL of placebo solution.

All patients will receive SC injections of fasinumab or fasinumab-matching placebo. Patients will be randomized to 2 treatment groups in a 1:1 ratio to receive either fasinumab 1 mg SC Q4W or fasinumab-matching placebo SC Q4W. All SC injections will be in the abdomen, thigh, or upper arm. Instructions for dose preparation and study drug administration are provided in the pharmacy manual. Patients will be observed in the clinic for approximately 1 hour after study drug is administered.

Doses of study drug must be given within ± 7 days from the scheduled dose date. If the window is missed, the dose should not be administered. The next dose should be administered at the next scheduled dosing date.

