10.4.4.5. Treatment Compliance

Overall treatment compliance is defined as the actual dose of injection compared to the prescribed dose of treatment during the treatment period up to treatment discontinuation. It is calculated according to the following formula:

100* Total actual injection dose taken/Prescribed injection dose.

The total number of actual doses of fasinumab will be summarized.

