5.6.2. Treatment Exposure

The treatment exposure to fasinumab and placebo SC doses will be calculated as:

- (Date of last administration of study drug - date of the first study drug administration after randomization) + 28

The duration of exposure will be summarized for each treatment group by descriptive statistics.

The number and percentage of patients randomized and exposed to double-blind study drug will be presented by specific time periods for each treatment group. The time periods of interest are specified as: ≥ 1 day, ≥ 29 days, ≥ 57 days, ≥ 85 days and ≥ 113 days.

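### SAP 5.6.1 names two different periods for the compliance denominator, and as they are most directly read both end relative to the last dose received, so doses missed at the end of treatment go partly or wholly uncounted

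*SAP*

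**What the plan says.** SAP 5.6.1 defines compliance twice. The prose takes injections received "divided by the expected number of SC injections during the on-treatment period up to treatment discontinuation". The displayed formula divides by the "Number of planned injections of study drug during the treatment exposure period", further limited to those "on or before the time that the patient discontinued from the treatment phase of the study".

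The two period names differ. SAP section 5 defines the on-treatment period as "the time from the first dose of study drug up to 28 days after the last dose of study drug". The treatment exposure period has no definition. The nearest text is SAP 5.6.2, which computes a duration of exposure: "Date of last administration of study drug - date of the first study drug administration after randomization) + 28".

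Protocol 10.4.4.5 defines compliance as the "actual dose of injection compared to the prescribed dose of treatment during the treatment period up to treatment discontinuation". Protocol 10.4.4 runs the treatment period to four weeks after the last dose and identifies that dose as the week-12 dose. The SAP's on-treatment definition does not carry over the week-12 marker. SAP 1.2.3 says only that the SAP is based on Amendment 2 and lists no modification.

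Doses can be missed without permanent discontinuation. Protocol 7.3.2.2 provides for temporary withholding, and protocol 7.1 says of a late dose: "If the window is missed, the dose should not be administered".

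**The concern.** A compliance denominator should come from the dosing schedule. Here the defined period, and the undefined one if it is read with 5.6.2, both end at a fixed distance from the last injection the patient actually received. A patient whose dosing lapses, and who is never recorded as permanently discontinued, therefore shortens his or her own denominator. The discontinuation limit in the formula does not repair this: it can only remove planned doses, never restore them. At stake is the accuracy of the reported compliance percentage, and whether two programmers working from 5.6.1 would produce the same figure.

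**Working it through.** The documents state no compliance figure, so there is none to reproduce. The check counts planned doses inside each candidate period.

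**Inputs**
- Planned doses: Days 1, 29, 57 and 85 (protocol Table 1; SAP Appendix 10.1).
- Exposure: last dose day − first dose day + 28 (SAP 5.6.2).
- On-treatment period: ends 28 days after the last dose (SAP section 5). SAP 5.8.2 starts post-treatment events more than 28 days after the last dose, so day last + 28 is inside.
- Dose window: ±7 days around the scheduled date (protocol 7.1).
- Assumptions: dose 1 given, no permanent discontinuation, and doses on the scheduled day unless stated otherwise.

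**Three readings of the denominator**
- A, formula read with 5.6.2: planned doses from Day 1 to Day 1 + exposure − 1, that is, to last dose + 27.
- B, prose read with section 5: planned doses up to last dose + 28.
- C, by schedule: all four planned doses.

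**Worked case, dose 1 only.** Exposure = 1 − 1 + 28 = 28 days. Under A the period is Days 1 to 28, Day 29 falls outside, and the score is 1/1 = 100%. Under B the period reaches 1 + 28 = Day 29, so dose 2 counts and the score is 1/2 = 50%. Under C it is 1/4 = 25%.

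| Doses received | A | B | C |
|---|---|---|---|
| 1 | 1/1 = 100% | 1/2 = 50% | 1/4 = 25% |
| 1, 2 | 2/2 = 100% | 2/3 = 67% | 2/4 = 50% |
| 1, 2, 3 | 3/3 = 100% | 3/4 = 75% | 3/4 = 75% |
| 1, 3 | 2/3 = 67% | 2/4 = 50% | 2/4 = 50% |
| 1, 4 | 2/4 = 50% | 2/4 = 50% | 2/4 = 50% |
| 1, 2, 4 or 1, 3, 4 | 3/4 = 75% | 3/4 = 75% | 3/4 = 75% |

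A dose missed between two given doses is counted under every reading. Only misses at the end are affected: A drops all of them, and B counts at most one.

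**Sensitivity to the dose window** (patient misses dose 4)
- Under B, dose 3 on Day 56 gives a period ending on Day 56 + 28 = 84. Day 85 is outside, so the score is 3/3 = 100%. Dose 3 on Day 57 gives an end on Day 85 and 3/4 = 75%.
- Under A, dose 3 on Day 57 gives an end on Day 57 + 27 = 84 and 100%. Dose 3 on Day 58 gives an end on Day 85 and 75%.

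The same applies earlier: with doses 1 and 2 only, dose 2 on Day 30 gives an end under A on Day 30 + 27 = 57, so Day 57 is inside and 100% becomes 2/3 = 67%.

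**The case against.** The strongest reply is that the 100% results rest on an inference. SAP 5.6.2 gives a duration; it does not name a treatment exposure period and does not refer to compliance. With on-schedule dosing, the formula's discontinuation limit would have nothing to do under reading A, because every later dose is already excluded. A reading that gives the limit work is the planned treatment period cut at discontinuation, which yields 25% for the one-dose patient and agrees with the protocol. This stands as a reason not to treat 100% as the only result. It does not clear the section: the prose names a period that is defined, and that period gives 50%.

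Two further points stand. For patients who permanently discontinue, both documents deliberately exclude later doses, so the problem is confined to holds or skipped doses at the end without discontinuation. The one-dose case is also extreme, since it needs three consecutive misses with no permanent stop, while the protocol routes holds towards restart or discontinuation. A missed fourth dose alone is a less extreme case, and on-schedule reading B already gives the schedule-based 75% for it.

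A reader might infer that the formula could hide under-exposure in the fasinumab arm and so colour a finding of no effect on nerves. The documents do not support that. SAP 5.6.1 also tabulates total injections and patients by number of injections received. SAP 5.6.2 reports exposure at "≥ 29 days, ≥ 57 days, ≥ 85 days and ≥ 113 days"; on-schedule exposures are 28, 56, 84 and 112 days for last doses 1 to 4, so each earlier last dose puts the patient one category lower. SAP 5.5.2 gives discontinuation reasons and a Kaplan-Meier plot. Compliance defines no analysis set and enters no model. Neither document gives a frequency of end-of-treatment misses, in total or by arm.

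**Conclusion.** The point holds as a definitional fault with limited impact. SAP 5.6.1 uses two period names, one undefined. The defined one ends relative to the last dose received, and so does the other if read with 5.6.2. Under those readings, and on-schedule dosing, compliance for a patient not permanently discontinued is overstated by 75 or 25 percentage points after dose 1 only (100% or 50% against 25%), by 50 or 17 points after doses 1 and 2, and by 25 or 0 points after doses 1 to 3. If the undefined term was meant as the planned treatment period, the formula is right and the prose is wrong. Either way the section does not fix one answer, and the defined on-treatment reading departs from the protocol without being listed as a change. It would be too strong to say that such patients are necessarily scored 100%, or that the summary is biased between arms.

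**What to change.** Use one denominator in both the prose and the formula of SAP 5.6.1: the injections scheduled (Days 1, 29, 57, 85) up to the earlier of permanent treatment discontinuation and the week-12 dosing visit, regardless of when the last dose was received. Delete the reference to the treatment exposure period, which appears in both terms of the formula. State whether doses withheld under protocol rules count as planned, or show them as a separate category; the SAP is silent on this at present, and the choice decides whether the figure measures adherence or dose delivery.

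If withheld doses count as planned, patients not permanently discontinued who stop after doses 1, 2 or 3 score 1/4 = 25%, 2/4 = 50% and 3/4 = 75%, and dose-window timing no longer affects the score. The cost is a wording change and a derivation that uses dates already collected. Reported compliance may be slightly lower.
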